APPENDIX X SUBJECTS CONTINUING PARTICIPATION AFTER MAIN STUDY

Add: new appendix title and text

APPENDIX X SUBJECTS CONTINUING PARTICIPATION AFTER MAIN STUDY

This appendix outlines the modifications to the study procedures and ABT-414 dosing in subjects who are currently receiving ABT-414 and who choose to continue ABT-414 treatment after the results from the pre-planned interim efficacy analysis. Subjects who received placebo will be discontinued from the study.

At the time of the interim efficacy analysis, there were approximately 48 subjects who remained on active ABT-414 treatment. The RTOG Steering Committee and AbbVie determined it was appropriate to allow subjects who are receiving ABT-414 to continue doing so based on investigator and subject decision.

Requirements for continuing treatment with ABT-414 after interim efficacy analysis

1. If the subject was receiving blinded treatment, they must be confirmed to be receiving ABT-414.
2. Must voluntarily sign and date the updated informed consent form, approved by an Independent Ethics Committee (IEC)/Institutional Review Board (IRB)

Study Activities

Only study activities necessary for study drug dosing, safety monitoring and adverse event reporting will be continued. The revised schedule of study assessments for these subjects is provided in Table 2b below.

Table 2b. Study Activities	28-Day Cycles ^a				Final Study Drug Visit ^d /At Progression	35-Day F/U ^e	49-Day F/U
	Day 1 of Every Cycle (1, 2, 3 etc.)	Day 1 of Odd-Numbered Cycles (1, 3, 5, etc.)	Day 15 of Every Cycle ^b	Day 22 of Every Cycle ^c			
Symptom-directed Physical Exam	X ^f		X ^f				
Ophthalmology Exam		X ^g				X ^g	X ^g
Chemistry	X				X	X	
Hematology	X			X	X	X	
Adverse Event Assessment/Concomitant Medications	X		X		X	X	X ^k
Temozolomide Administration	X ^h						
ABT-414 Administration	X ⁱ		X ⁱ				
Prophylactic Eye Drop Administration	X ^j		X ^j				

F/U = Follow-up

- a. Assessments will be based on 28-day treatment cycles, with the first cycle starting approximately 4 weeks after completion of radiation therapy. Subjects will receive concomitant TMZ and study drug (ABT-414) for the first 6 cycles, and study drug monotherapy for an additional 6 cycles or until disease progression or study drug discontinuation.
- b. Day 15 visit will not be performed after discontinuation of study drug (ABT-414) treatment.
- c. As per TMZ prescribing information, during the 28-day cycle of TMZ, a blood count for ANC and platelets should be performed 21 days (\pm 2 days) after the start of each TMZ cycle. If the ANC falls below 1,500/ μ L or if the platelet count falls below 100,000/ mm^3 , then blood counts should be performed weekly until recovery to these levels before TMZ dosing. A certified local lab may be used instead of central lab; if so, ANC and platelet results should be reported in the eCRF. Day 22 testing may be omitted for cycles in which TMZ is not administered or if local prescribing information allows for a different testing schedule for ANC and platelets.
- d. Final Study Drug Visit to be performed approximately 14 days after last dose of ABT-414.
- e. To be performed 35 days (\pm 3 days) after the last dose of study drug (ABT-414). If the Final Study Drug Visit is more than 35 days after the last dose of study drug, then 35-day safety follow-up procedures will not be performed.
- f. Physical exams will be performed only as needed for safety management and adverse event reporting.
- g. Ophthalmology exams will be performed only as needed for safety management and AE/SAE reporting. The last ophthalmology exam following discontinuation of ABT-414 may be done at the 35-Day F/U or 49-Day F/U Visit. Targeted ophthalmology exam data will not be collected by the Sponsor.
- h. TMZ will be administered once daily on Days 1 through 5 of each 28-day cycle for 6 cycles per the local prescribing information.
- i. ABT-414 infusion will be administered on Day 1 and Day 15 of each 28-day cycle for 12 cycles.
- j. Prophylactic eye drops will be administered daily for 7 days with each dose of ABT-414, from 2 days before until 4 days after each dose of study drug (ABT-414), as described in Section 5.5 of the main study. Patients will receive management of ocular side effects as per investigator discretion. In this case, ABT-414 dose interruption and/or reduction may be used, and any available prophylactic or supportive care measures may be employed without restriction, at the discretion of the investigator.
- k. If the subject is unable to return to the site for the Day 49 Follow Up Visit, a phone call may be conducted to obtain AE/SAE and concomitant medication information.

ABT-414 Administration and Individual Subject Discontinuation

ABT-414 will be administered as described in the main protocol.

1.0 Title Page

Statistical Analysis Plan

Study M13-813

**A Randomized, Placebo Controlled Phase 3 Study of
ABT-414 with Concurrent Chemoradiation and
Adjuvant Temozolomide in Subjects with Newly
Diagnosed Glioblastoma (GBM) with Epidermal
Growth Factor Receptor (EGFR) Amplification
(Intelligence1)**

Date: 23 Apr 2019

Version 2.0

Prepared in collaboration by

 AbbVie

and

 RTOG Foundation

Document history

Statistical Analysis Plan	Date
Original (version 1.0)	03-Dec-2018
Amendment 1 (version 2.0)	23-Apr-2019

Summary of changes in Amendment 1 (version 2.0)

- The definition of deterioration in HVLt-R Total recall score has been updated to use 5-point change in raw score.

Rationale: To match the deterioration definition used in prior RTOG studies (Wefel et al).

- The censoring rule for the PFS analysis was updated to exclude any PD or death that occurs > 20 weeks after the previous scan date.

Rationale: To avoid prolonging PFS estimates when there are missing RANO assessments. The 20-week window was chosen to reflect 2 consecutive missed RANO assessments (8-week intervals) plus the 4-week assessment window specified in the study protocol.

- Additional sensitivity analyses for PFS including investigator assessed PFS and PFS with varying censoring rule and are included.

Rationale: These additional sensitivity analyses for centrally assessed PFS are included to evaluate the robustness of the primary PFS analysis. In addition, investigator assessed PFS analysis is also included.

- Visit windows for different endpoints were clarified with greater details.

Rationale: The details were added to provide appropriate information in the SAP for clarification purpose, including providing windows suitable for the procedure schedule for different endpoints.

- Other changes: Following changes are also implemented:
 - Editorial changes to improve consistency and clarity.
 - Analysis related to targeted ophthalmologic evaluation (TOE) endpoints are updated
 - Definition of prior medication is updated to include medications that started before first study treatment and continue to be taken after first study treatment.
 - Questionnaire of COWA-FAS added in the Appendix VI.

3.0 Abbreviation

AE(SI)	Adverse Event (of Special Interest)
ALP	Alkaline Phosphatase
ALT	Alanine Aminotransferase
ANC	Absolute Neutrophil Count
ANCOVA	Analysis of Covariance
AST	Aspartate Aminotransferase
CI	Confidence Interval
COWA-FAS	Controlled Oral Word Association – FAS version
CTC(AE)	Common Terminology Criteria (for Adverse Events)
Depatux-M	Depatuxizumab mafodotin
DFS	Deterioration Free Survival
ECG	Electrocardiogram
eCRFs	Electronic Case Report Forms
EGFR	Epidermal Growth Factor Receptor
EORTC	European Organization for Research and Treatment of Cancer
EQ-5D-5L	EuroQol 5 Dimensions 5 Level
EQ VAS	EuroQol Visual Analog Scale
FAS	Full Analysis Set
FH	Fleming Harrington
FLAIR	Fluid Attenuated Inversion Recovery
GBM	Glioblastoma
GGT	Gamma-glutamyl transferase
Gy	Gray
HR	Hazard Ratio
HRQoL	Health Related Quality of Life
HVLT-R	Hopkins Verbal Learning Test-Revised
IDMC	Independent Data Monitoring Committee
IRT	Interactive Response Technology
KM	Kaplan Meier
KPS	Karnofsky Performance Status
LLN	Lower Limit of Normal
MDASI-BT	M.D. Anderson Symptom Inventory Brain Tumor Module

MedDRA	Medical Dictionary for Regulatory Activities
MGMT	O6-methylguaninemethyltransferase
MRI	Magnetic Resonance Imaging
NCI	National Cancer Institute
NEI-VFQ-25	National Eye Institute Visual Functioning Questionnaire – 25
OS	Overall Survival
PD	Progressive Disease
PFS	Progression-Free Survival
PPS	Per-protocol Set
PRO	Patient-Reported Outcomes
PT	Preferred Term
QLQ-BN20	Quality of Life Questionnaire Brain Cancer Module
QLQ-C30	Quality of Life Questionnaire Core 30
QoL	Quality of Life
RANO	Response Assessment in Neuro Oncology
RCI	Reliable Change Index
ROW	Rest of the World
RT	Radiation Therapy
RPA	Recursive Partitioning Analysis
RS	Raw Score
RTOG	RTOG Foundation
SAE	Serious Adverse Event
SAP	Statistical Analysis Plan
SAS	Safety Analysis Set
SGPT	Serum glutamic-pyruvic transaminase
SGOT	Serum glutamic-oxaloacetic transaminase
SOC	Standard of Care
SS	Scale Score
TE(AE)	Treatment Emergent Adverse Event
TMZ	Temozolomide
TOE	Targeted ophthalmology exam
TTE	Time to Event
ULN	Upper Limit of Normal
WHO	World Health Organization

4.0 Introduction

This statistical analysis plan (SAP) will provide details statistical methods for the analysis of efficacy and safety data collected in Study M13-813 (INTELLANCE 1) as outlined in Protocol Amendment 8 (dated 29 November 2018)²¹ and will describe analysis conventions to guide the statistical programming work.

Efficacy and safety analyses will be performed using SAS Version 9.3 or higher (SAS Institute, Inc., Cary, NC 27513) under the UNIX operating system. The SAP will be signed off before any unblinded analysis is performed.

5.0 Study Objectives, Design and Procedures

5.1 Objectives

Primary objective

To determine whether the addition of Depatuxizumab mafodotin or Depatux-M (ABT-414) to concomitant radiotherapy (RT) and Temozolomide (TMZ) as well as to adjuvant TMZ prolongs Overall Survival (OS) among subjects with newly diagnosed glioblastoma (GBM) harboring epidermal growth factor receptor (EGFR) amplification.

Secondary objectives

To determine whether the addition of Depatux-M to concomitant RT and TMZ as well as to adjuvant TMZ improves outcomes among subjects with newly diagnosed GBM harboring *EGFR* amplification in terms of the following endpoints:

- Progression Free Survival (PFS), assessed centrally
- OS for the MGMT unmethylated group
- OS for the MGMT methylated group
- Deterioration Free Survival in M.D. Anderson Symptom Inventory Brain Tumor Module (MDASI-BT) symptom severity score
- Deterioration Free Survival in MDASI-BT symptom interference score

- Deterioration Free Survival in Hopkins Verbal Learning Test Revised (HVLTR) Total Recall score
- OS for the *EGFRvIII*-mutated tumor subgroup
- PFS for *EGFRvIII*-mutated tumor subgroup

Safety:

- Assessment of comparative safety

Exploratory objectives

To determine whether the addition of Depatux-M to concomitant RT and TMZ as well as to adjuvant TMZ improves outcomes among subjects with newly diagnosed GBM harboring *EGFR* amplification in terms of the following endpoints:

- OS at 0.5, 1, 2, 2.5, 3, 4, and 5 years
- Centrally-assessed PFS at 0.5, 1, 2, 2.5, 3, 4, and 5 years
- Centrally-assessed PFS for the MGMT unmethylated and methylated subgroups
- OS and centrally-assessed PFS for non-*EGFRvIII* mutated subgroup
- OS and centrally-assessed PFS for Total EGFR expression levels
- Progression Free Survival (PFS), assessed by investigator
- *EGFRvIII* status as a prognostic factor independent of treatment assignment overall and among molecular subgroups
- Change from baseline in HRQoL and health status measures
 - QLQ-C30: Global health status, Physical Functioning, Cognitive Functioning, and Role Functioning scale
 - QLQ-BN20: Visual Disorder, Motor Dysfunction, and Communication Disorder scale
 - MDASI-BT: neurologic, cognitive, treatment, symptom interference (activity-related, mood-related), and vision item scores
 - COWA-FAS: verbal fluency score

- HVLT-R: Total Recall score, Delayed Recall Score, Recognition Discrimination Index
- EQ-5D-5L and EQ VAS scale scores
- Karnofsky Performance Status (KPS)
- Median time for which KPS score was maintained at 70 or higher
- Deterioration Free Survival in neurocognitive functioning on Controlled Oral Word Association (COWA-FAS)
- Changes in EGFR molecular profile during therapy among subjects who undergo additional surgery as part of routine care
- Pharmacokinetics of Depatux-M, total ABT-806, and free cys-mcMMAF
- Change from baseline in corticosteroid dosing

5.2 Study Design

5.2.1 Study Design and Design Diagram

This is a Phase 3 randomized double-blind, placebo-controlled trial comparing the efficacy and safety of Depatux-M versus placebo, each as concurrent treatment with standard-of-care therapy (comprised of concomitant RT/TMZ and adjuvant TMZ) and followed by monotherapy, in subjects with newly diagnosed GBM. For this study, subjects will be stratified by MGMT methylation status (methylated and unmethylated), RPA class (III, IV, and V), region of the world (North America (includes USA and Canada) and rest of the world (ROW)) and EGFRvIII mutation status (mutated and wild type/indeterminate). A total of 640 evaluable subjects will be randomized on a 1:1 ratio to receive:

- Arm A: Depatux-M plus TMZ during the Chemoradiation and Adjuvant Phases.
- Arm B: Placebo plus TMZ during the Chemoradiation and Adjuvant Phases.

The study comprises the following 4 phases/periods: a Screening Period, followed in sequence by a Chemoradiation Phase, an Adjuvant Phase and a Follow-up Phase.

Screening Period

Screening procedures must be completed prior to Day 1 of the Chemoradiation Phase. The baseline brain magnetic resonance imaging (MRI) will be obtained no more than 28 (but preferably fewer) days prior to Day 1 of the Chemoradiation Phase. Safety related evaluations will be conducted 14 or fewer days prior to Day 1 of the Chemoradiation Phase. If a subject has a repeat surgery prior to randomization, the extent of surgical resection after the repeat surgery (biopsy-only vs. partial/total resection) will be used for determining RPA class.

Chemoradiation Phase

Treatment in the Chemoradiation Phase should begin ≤ 7 weeks after surgery/biopsy. During this Phase, all subjects will undergo fractionated focal radiotherapy (RT), with one treatment of approximately 2 gray (Gy) given daily 5 days per week for a total of approximately 60 Gy over approximately 6 weeks (and no more than 7 weeks). TMZ will be administered continuously from Day 1 of radiotherapy to the last day of radiation at a daily oral dose of 75 mg/m² for a maximum of 49 days. Subjects will receive blinded Depatux-M or Placebo at 2.0 mg/kg IV infusion over 30 – 40 minutes once every 2 weeks (Day 1 of Weeks 1, 3, and 5 of the 6-week regimen).

Adjuvant Phase

The Adjuvant Phase is comprised of 28-day cycles. The first cycle starts approximately 28 days after the last day of radiotherapy. Subsequent cycles will start approximately 28 days from the start of the previous cycle. Subjects receives concomitant TMZ (on Day 1 - 5) and Depatux-M/Placebo (on Day 1 and Day 15) for the first 6 cycles, and study drug (Depatux-M/Placebo) monotherapy for the following 6 cycles. TMZ treatment for an additional 6 cycles (up to 12 cycles total) is allowed at investigator discretion. If after completing 12 cycles of adjuvant treatment, the subject is tolerating study drug (Depatux-M or placebo) and the investigator believes the subject is continuing to benefit from ongoing study drug treatment, the investigator may extend the Adjuvant Phase after consultation with the Neuro-Medical Oncology Chair or AbbVie Medical Monitor, as

long as subject's disease has not progressed. Adjuvant treatment will be discontinued once disease progression occurs. A final study drug visit will be performed upon discontinuation of study drug (Depatux-M/placebo) for any reason, followed by a 49-Day Follow-Up Visit (± 3 days).

[figure not shown]
Follow-Up Phase

Subjects who complete adjuvant treatment or discontinue study drug prior to disease progression will continue to undergo MRI assessment, assessment of neurocognitive functioning, and assessment of PROs approximately every 8 weeks up to and including the time of disease progression. After disease progression, overall survival will continue to be assessed quarterly.

Doses of study drug (i.e., Depatux-M/Placebo and TMZ) in chemoradiation and adjuvant phases can be modified or interrupted (see Protocol Section 8.1, Section 8.2 and Section 8.3). Post-baseline scans will be obtained ≤ 14 days before Day 1 of each odd-numbered cycle (Cycles 1, 3, 5, etc.) of the Adjuvant Phase and ≤ 14 days before each visit (approximately every 8 weeks) of the Follow-Up Phase. OS will be assessed quarterly after study discontinuation.

A schematic of the study design is shown in [Figure 1](#). The study activities for each visit in Chemoradiation and Adjuvant phases are outlined in [Table 1](#) and [Table 2](#) of study protocol, respectively.

Figure 1. Schema of study design

5.2.2 Variables used for Stratification at Randomization

All screening activities must be completed and reviewed prior to randomization. Subjects who meet the eligibility criteria will be stratified according to the following 4 factors:

- *MGMT* methylation status: Methylated and Unmethylated
- RPA classes: III, IV, and V
- Region of the World: North America (includes USA and Canada) and Rest of the World (ROW)
- *EGFRvIII* status: Mutated and Other.

EGFRvIII Other includes wild type, indeterminate due to test failure, invalid, or insufficient tissue. Within each stratum, subjects will be randomized to either Arm A (i.e.,

Depatux-M + TMZ) or Arm B (i.e., Placebo + TMZ) in a 1:1 ratio via the interactive response technology (IRT) system.

Screening numbers will be unique 5-digit numbers with the first 3 digits representing the investigative site, and the last 2 digits representing the subjects at that site. Randomized subjects will keep their screening number as their subject identification number. During randomization each patient will receive a separate unique 6 digit randomization number. This randomization number will be recorded automatically in the electronic case report forms (eCRFs) through the IRT system.

5.3 Endpoints

5.3.1 Primary Efficacy Endpoint

Primary efficacy endpoint is overall survival (OS). OS is defined as time from the randomization to death due to any cause. For subjects who are alive at the end of this study, OS will be right-censored on the last date the subject is known to be alive.

5.3.2 Secondary Efficacy Endpoints

Overall Survival (OS) related secondary endpoint

The following OS related endpoints are considered as secondary endpoints:

- OS for the MGMT unmethylated group
- OS for the MGMT methylated group
- OS for the *EGFRvIII*-mutated tumor subgroup

Progression Free Survival (PFS) related endpoints

PFS is defined as time from randomization to the date of progression of disease (PD) assessed centrally per Response Assessment in Neuro-Oncology (RANO) criteria or death, whichever occurs first. Any PD or death that occurs > 20 weeks after the previous scan date will be excluded along with the following scans. Subjects without an event will be right-censored at the date of last follow up for disease progression. Patients with no

post baseline follow up for progression and who doesn't experience a death event within 20 weeks after the randomization date will be censored at the day of randomization.

The PFS related secondary endpoints are:

- PFS, assessed by independent central review
- PFS, assessed by independent central review for *EGFRvIII*-mutated tumor subgroup

MDASI-BT symptom severity and interference score

This is a validated PRO instrument used to assess the severity of brain tumor related symptoms and its impact on daily function in last 24 hours. It consists of 22 symptom items and 6 interference items. Each item is rated from 0 to 10, with higher score indicating worse symptoms/interference.

MDASI-BT symptom severity score is defined as average over 13 core symptom items and 9 brain tumor symptom items. The MDASI-BT symptom severity score will be obtained if more than 50% of the items (at least 12 out of 22 items) are completed on a given assessment using the formula: (sum of items answered) \times 22/number of items answered.

MDASI-BT symptom interference score is defined as an average of 6 interference items. The MDASI-BT symptom interference score will be obtained if more than 50% of the items (at least four out of six items) are completed on a given assessment using the formula: (sum of items answered) \times 6/number of items answered.^{18,28}

A change of ≥ 1 point on a 10-point scale at follow-up assessment with respect to baseline will be considered as clinically relevant. Changes in symptom severity score and symptom interference score at each time point will be classified into 3 categories: improved (≤ -1), stable (> -1 and < 1), and deteriorated (≥ 1).

The secondary endpoints based on this measure are as follows:

- Deterioration Free Survival (i.e., decrease by 1 unit or death, whichever comes first) in MDASI-BT symptom severity score
- Deterioration Free Survival (i.e., decrease by 1 unit or death, whichever comes first) in MDASI-BT symptom interference score

HVLT-R

This standardized neurocognitive function test is used to assess change in verbal memory over time. This test has been validated within brain-disordered population. The HVLT-R Total Recall Score will be computed by summing the total number of words across 3 trials (Trial 1, Trial 2 and Trial 3). Then, the Total Recall Score will be standardized using the published age specific normative data from a healthy population.

A change of ≥ 5 points in raw HVLT-R total recall score with respect to baseline will be considered as clinically relevant. Changes in HVLT-R total recall score at each post-baseline time point will be classified into 3 categories: deteriorated (≤ -5), stable (> -5 and < 5) and improved (≥ 5) (Wefel et al., 2011).

The secondary endpoint based on this measure is:

- Deterioration Free Survival in HVLT-R total recall score.

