- A laboratory test value that requires a subject to be discontinued or interrupted from any study treatment agent (ABT-414, TMZ or RT) or from the study, or requires a subject to receive treatment (medical intervention) will be recorded as an adverse event.

MRI and Clinical Assessment for Disease Progression

A brain MRI scan with and without contrast, performed at any time after diagnostic surgery or biopsy but prior to randomization, is required to serve as a baseline scan for RANO tumor response assessments. The most recent scan done prior to randomization will be used as the baseline scan. A baseline MRI must include the image sequences (T1 with and without contrast and T2 FLAIR) required for making RANO assessments. If a subject starts chemoradiation ≤ 28 days after surgery, the post-operative MRI scan (including an intraoperative or post-operative MRI scan) performed as part of standard care prior to Screening may be used as

the baseline scan for RANO assessments; if so, this scan must be included with the submission of scans for central imaging reviews. If the subject starts chemoradiation more than 28 days after surgery, then the baseline MRI must be performed within 21 (preferably fewer) days prior to Day 1 Week 1 of Chemoradiation and must allow sufficient time to revise the radiation therapy plan if needed due to a significant change in tumor since surgery.

Post-baseline MRIs with contrast will be obtained ≤ 14 days before Day 1 of each odd-numbered cycle (Cycles 1, 3, 5, etc.) of the Adjuvant Therapy Phase; approximately every 8 weeks of the Follow-Up Phase (≤ 14 days before each Follow-Up Visit), and at the Final Study Drug Visit (if the subject withdraws from the study prior to disease progression and has not had an MRI with contrast within the previous 3 weeks). At the discretion of the Investigator, MRI with contrast may be performed at additional times as clinically indicated or as needed to assess whether there has been progression of disease. If the subject discontinues study drug prior to disease progression, every effort should be made to acquire MRIs according to the same schedule while the subject is willing.

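### The 20-week PFS gap rule does not fit the first scan interval: it can drop a progression after one missed scan, and its precedence over a second, randomization-based 20-week rule is not stated

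*SAP*

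**What the plan says.** SAP 5.3.2 defines PFS by central RANO assessment and adds: "Any PD or death that occurs > 20 weeks after the previous scan date will be excluded along with the following scans". The next provisions censor subjects without an event at their last follow-up for progression. They then deal separately with patients who have no "post baseline follow up for progression and who doesn't experience a death event within 20 weeks after the randomization date will be censored" at randomization. The first count starts at the previous scan and the second at randomization. The paragraph does not say whether the baseline MRI is a previous scan, or which sentence governs when both apply.

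The summary of changes for SAP version 2.0 gives the reason for the limit: "The 20-week window was chosen to reflect 2 consecutive missed RANO assessments (8-week intervals) plus the 4-week assessment window specified in the study protocol".

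SAP 5.2.1 sets the scan schedule: "Post-baseline scans will be obtained ≤ 14 days before Day 1 of each odd-numbered cycle (Cycles 1, 3, 5, etc.) of the Adjuvant Phase". On the baseline scan, Protocol 4.2 says: "The most recent scan done prior to randomization will be used as the baseline scan".

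SAP 10.5 has two PFS sensitivity analyses. The first has no gap rule. The second again equates more than 20 weeks with two or more missed assessments, and dates the imputed progression at the last scan plus 8 weeks.

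**The concern.** The limit is meant to pick out patients with two consecutive missed scans. It assumes that scans are 8 weeks apart, but the first two are not. Between the baseline MRI and the Cycle 1 scan lie the baseline lead time, chemoradiation and the rest period. One missed scan can therefore use up an allowance meant for two. If the excluded event is a progression on the Cycle 3 scan, no earlier post-baseline scan remains, and the patient is censored at randomization.

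Patients too ill for the Cycle 1 scan are plausibly those with early events, so this censoring could be informative. Centrally assessed PFS is second in the testing hierarchy (SAP 5.6.2), and PFS in the EGFRvIII-mutated subgroup inherits the definition. Separately, two programmers could treat the same early death differently, because the paragraph uses two starting points.

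**Working it through.** **The plan's own figure.** 2 × 8 + 4 = 20 weeks, which reproduces. With m missed scans in the regular part, and each scan 0 to 14 days early, the gap is 8(m + 1) ± 2 weeks. That is 14 to 18 weeks for one missed scan and 22 to 26 for two, so 20 weeks separates them correctly.

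**Inputs for the first interval.**
- Baseline MRI lead before Day 1: 0 to 21 days if chemoradiation starts more than 28 days after surgery (Protocol 3.0 and 4.2). Otherwise a post-operative scan is allowed, so up to 28 days. SAP 5.2.1 allows 28 days.
- Radiotherapy: 6 weeks, at most 7 (SAP 5.2.1).
- Rest: about 28 days. Protocol 5.1 asks for notification only beyond 42 days.
- Cycle 3 starts 56 days after Cycle 1; scans are 0 to 14 days early.

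**Formula.** Gap to the Cycle 3 scan = lead + radiotherapy + rest + 56 − days early. The limit is 140 days.

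| Schedule | Weeks from Day 1 | From baseline, lead 0–21 days | Maximum, lead 28 days |
|---|---|---|---|
| Nominal (6 + 4 weeks) | 16–18 | 16–21 | 22 |
| 7-week radiotherapy | 17–19 | 17–22 | 23 |
| 42-day rest | 18–20 | 18–23 | 24 |
| Both | 19–21 | 19–24 | 25 |

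Nominal maximum: 28 + 42 + 28 + 56 − 0 = 154 days. Delayed maximum: 28 + 49 + 42 + 56 = 175 days.

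On the nominal schedule, a Cycle 3 scan done on Day 1 passes the limit only if the lead exceeds 140 − 126 = 14 days. A scan 7 days early needs a lead above 21 days. With no missed scan the gap is at most 17 weeks, so nothing is excluded.

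**Share over the limit, given that only the Cycle 1 scan is missed.** Weighting all whole-day combinations of lead and scan earliness equally on the nominal schedule gives 28/330 = 8.5% for leads of 0 to 21 days and 105/435 = 24.1% for 0 to 28 days. With 7-week radiotherapy the figures are 31.8% and 48.3%. The equal weighting is an assumption.

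**The two starting points for deaths.** Take a patient with no post-baseline scan, a baseline MRI 21 days before randomization, and death at week 18. That is 21 weeks after the scan, so the first sentence excludes the death. It is within 20 weeks of randomization, so the second sentence implies that it counts. The window runs from 20 weeks minus the lead to 20 weeks, so it is at most 3 to 4 weeks wide.

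To bound its size, assume exponential OS with the SAP's 16-month control median: S(d) = exp(−ln 2 × (d/30.4375)/16). Then S(119) − S(140) = 2.5% for a 21-day lead and S(112) − S(140) = 3.3% for 28 days. That is about 16 to 21 of 639 if every patient had that lead. Only those among them without a post-baseline scan are affected.

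**Sensitivity analysis 2.** Last scan plus 8 weeks, counted from a baseline scan 0 to 4 weeks before Day 1, falls 4 to 8 weeks after Day 1. The first scan is planned for weeks 8 to 10.

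**The case against.** Five points weigh on the other side.

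- **Sensitivity analyses exist.** Analysis 1 counts every progression and death with no gap rule, so the effect of the rule will be visible. This stands. Analysis 2 is less help, because it carries the same 20-week equivalence.
- **The death sentences may not conflict.** The sentence on patients with no post-baseline follow-up can be read as the special case that replaces the scan date with randomization. On that reading the conflict disappears. A reader might infer a flat contradiction, but the documents support only an unstated precedence.
- **RANO narrows the progression case.** On the nominal schedule the Cycle 3 scan falls 28 + 56 − (0 to 14) = 70 to 84 days after radiotherapy. Within 12 weeks, imaging can define progression only by new enhancement outside the radiation field. The later 25% criterion compares with the first post-radiotherapy scan, which is missing here, although Protocol 6.1 also mentions comparison with baseline. This shrinks the scenario considerably. It shrinks it less with a 42-day rest, when the scan falls 84 to 98 days after radiotherapy.
- **The shares are conditional.** A reader might take 24% or 48% as the share of trial patients losing an event. The documents do not support that. The figures apply only to patients who miss the Cycle 1 scan, whose number is not given, and extra clinically indicated MRIs would reset the clock.
- **It is late to change the rule.** Protocol 1.0 reports an unblinded interim with one-sided p = 0.628 for OS. Under the fixed sequence, PFS could not be declared significant at that analysis. This stands and limits the fix.

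**Conclusion.** The point holds in a limited form. Read literally, with baseline as the previous scan, the 20-week rule can exclude a progression after one missed scan in the first interval, against its own rationale. The Cycle 3 scan lies 16 to 22 weeks after baseline nominally, and up to 25 weeks with delays. This is not automatic, since a lead of 14 days or less keeps the event on the nominal schedule. On the literal text, the unstated precedence also leaves deaths ambiguous over at most 3 to 4 weeks.

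The number affected is probably small. If previous scan meant post-baseline scans only, both problems would go, but a late progression on a first scan would then have no gap rule. The SAP does not adopt that reading. Nor do the documents show that reported PFS is biased, or that the rule favours either arm.

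**What to change.** Define the exclusion as progression or death after two or more consecutive planned scans have been missed. Where baseline is the only earlier scan, use one randomization-based limit for both progression and death, and state that it replaces the previous-scan rule. With scans planned at about weeks 10 and 18, the SAP's own logic gives 10 + 8 + 4 = 22 weeks.

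This limit separates the cases. With one missed scan, the Cycle 3 scan is at most 21 weeks from Day 1 on the delayed schedule, or 21.4 from randomization if that was 3 days earlier, so the event is kept. With two missed scans, the Cycle 5 scan is at least 24 weeks from Day 1, so the event is excluded. Moving the present 20 weeks to randomization would still drop the event in the 21-week case. The 22-week limit also covers patients who never start adjuvant therapy, for whom no Cycle 1 date exists.

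Align sensitivity analysis 2, including its imputed date in the first interval. Because the interim has been unblinded, report this version beside the pre-specified one for that analysis and do not substitute it. The cost is a wording change and a small programming change.
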